6.2 Round 2 Intervention

The intervention round consists of 8 EsoGuard patient cases (clinical vignettes) (3 positive and 5 negative for EsoGuard). The 3 questionnaires (A/B/C) will have the same 5 negative EsoGuard cases, and 1 (different) positive EsoGuard case per questionnaire.

The following questions will be asked per clinical vignette:

1. What level of risk for BE (and/or EC) do you think this patient has?
 - Low
 - Intermediate
 - High
2. Do you refer this patient for upper endoscopy?
 - Yes, I would refer this patient for endoscopy
 - No, I would not refer this patient for endoscopy
3. Did the EsoGuard result influence your decision to refer or not refer the patient for upper endoscopy?
 - Yes; the EsoGuard result had an impact on my decision
 - No; the EsoGuard result had no impact on my decision

The following self-assessment questions will be asked of each participant at the end of round two (scale 1 very low to 5 high):

- Rate your understanding of EsoCheck/EsoGuard and its indications?
- How likely are you to use EsoCheck/EsoGuard for BE screening in your own practice?
- How likely are you to refer this technology to others or use in their practices?

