3. TRIAL DESIGN

This will be a prospective randomized, controlled, virtual, patient study to measure the impact of EsoCheck/EsoGuard on health care provider's decision for upper endoscopy referral.

Around 200 US physicians will be asked to participate in this study and at least 100 will be enrolled.

[figure not shown]
Physicians eligible for participation are those whose scope of practice includes preventative care and disease screening – namely screening of BE, such as primary care physicians, family medicine physicians, and general practitioners; physicians whose scope of practice include diagnosis and management of esophageal disease may also participate.

- At least 80% of the overall study population will be primary care primary care physicians, family medicine physicians, and general practitioners;
- ≤20% will be other physicians/specialists.

Eligible participants will sign the IRB approved ASBE participant Informed Consent Form (ICF).

The participants will complete two rounds of questions concerning the assessed risk for BE and decision for endoscopy referral of 6 patient cases (clinical vignettes). Per round, there will be 3 different questionnaires consisting of 6 clinical vignettes (A/B/C). Participants will be randomized to questionnaire A, B or C according to the randomization scheme. The link to the online questionnaires will be sent by email. The questionnaires should be completed within approximately ten (10) business days, and no more than twenty (20) business days after receiving the link. After the first round has been completed, an EsoCheck/EsoGuard educational information package and the second round of 6 clinical vignettes including EsoGuard results will be sent.

Flowchart

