6. STUDY PROCEDURES

The participants will complete two rounds of questions concerning the assessed risk for BE and upper endoscopy referral of 6 patient cases (clinical vignettes). Per round, there will be 3 different questionnaires consisting of 6 clinical vignettes (A/B/C). Participants will be randomized to questionnaire A, B or C according to the randomization scheme.

The link to the online questionnaires will be sent by email. The questionnaires should be completed within approximately ten (10) business days, and no more than twenty (20) business days after receiving the link.

After the first round has been completed, an EsoCheck/EsoGuard information package and the second round of 6 clinical vignettes including EsoGuard results will be sent.

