6.1 Round 1 Control

The control round consists of 8 virtual patient cases (clinical vignettes). The 3 questionnaires (A/B/C) will consist of 6 clinical vignettes with the same risk profile as in the intervention round with a different description and in a different order.

The following baseline and self-assessment questions will be asked:

- Location of practice
- Type of practice
- Number of MDs associated with the practice
- Years of practice
- Proportion of patients covered by Medicare/Commercial insurance (<50% Medicare/>50% commercial; 50/50; >50% Medicare/<50% commercial)
- Estimate of number of GERD patients seen per week (<10; 10-20; ≥20)
- Rate your knowledge of Barrett's Esophagus (BE), esophageal adenocarcinoma (EAC), and associated risk factors (1 = not knowledgeable at all; 2 = not very knowledgeable; 3 = somewhat knowledgeable; 4 = very knowledgeable; 5 = expert)
- Rate your knowledge of the options and indications for BE screening (1 = not knowledgeable at all; 2 = not very knowledgeable; 3 = somewhat knowledgeable; 4 = very knowledgeable; 5 = expert)
- Rate the frequency in which you refer your GERD patients for endoscopic BE screening, as part of your standard practice (<20%; 20-40%; 40-60%; 60-80%; ≥80%)

The following questions will be asked per clinical vignette:

1. What level of risk for BE (and/or EC) do you think this patient has?
 - Low
 - Intermediate
 - High
2. Do you refer this patient for upper endoscopy?
 - Yes, I would refer this patient for endoscopy
 - No, I would not refer this patient for endoscopy

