7.3 Statistical formulation and statistical analysis plan of the objectives

Primary objective: To determine the impact of EsoCheck/EsoGuard on health care provider's decision for upper endoscopy referral.

The impact will be measured by assessing the change in the percentage/rate of virtual patient cases who will be referred for endoscopy in the intervention round compared to the control round.

Statistics summarizing the agreement between the EsoGuard result (positive or negative) and the health care provider's decision (referral or no referral deemed necessary) include:

- positive agreement; percentage of EsoGuard positive virtual patient cases that were referred for endoscopy
- negative agreement; percentage of EsoGuard negative virtual patient cases that were not referred for endoscopy
- positive predictive value (PPV); percentage of referred virtual patient cases that are EsoGuard positive
- negative predictive value (NPV); percentage of non-referred virtual patient cases that are EsoGuard negative
- percentage of concordance

The participant-reported impact of EsoGuard results on their clinical decision making will be measured by assessing the proportion of patient cases in round 2 for which the provider answered the question, *“Did the EsoGuard result influence your decision to refer or not refer the patient for upper endoscopy”*, with, *“Yes; the EsoGuard result had an impact on my decision”* divided by all patient cases in round 2.

The provided answers will also be reported in a table with counts and percentages.

Secondary objective: To determine the impact of EsoCheck/EsoGuard on health care provider's patient risk assessment for BE.

The impact will be measured by assessing the change in the provider's virtual patient risk assessment for BE in the intervention round compared to the control round.

The provided answers will be reported in a table with counts and percentages.

The baseline and self-assessment questions, Round 1 Control, and Round 2 Intervention, will be reported in a table with counts and percentages.

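### In Round 2 each case carries one fixed EsoGuard result, so the agreement statistics and the positive-versus-negative contrast cannot be separated from case profile

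*Combined protocol and SAP*

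**What the plan says.** Section 6.2 sets up the Round 2 pool: "The intervention round consists of 8 EsoGuard patient cases (clinical vignettes) (3 positive and 5 negative for EsoGuard". It then allocates the cases to versions: "The 3 questionnaires (A/B/C) will have the same 5 negative EsoGuard cases, and 1 (different) positive EsoGuard case per questionnaire". Each physician thus sees 5 + 1 = 6 cases. The only randomization is to a version (section 3): "Participants will be randomized to questionnaire A, B or C according to the randomization scheme".

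Round 1 is described in section 6.1. Each version holds "6 clinical vignettes with the same risk profile as in the intervention round with a different description and in a different order", shown without a test result. The order of rounds is the same for everyone (section 6): "After the first round has been completed, an EsoCheck/EsoGuard information package and the second round of 6 clinical vignettes including EsoGuard results will be sent".

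Under the primary objective, section 7.3 measures impact as the "change in the percentage/rate of virtual patient cases who will be referred for endoscopy in the intervention round compared to the control round". Under the same objective it lists agreement statistics for the result and the referral decision, among them "positive agreement; percentage of EsoGuard positive virtual patient cases that were referred for endoscopy" and "negative agreement; percentage of EsoGuard negative virtual patient cases that were not referred for endoscopy", together with PPV, NPV and overall concordance. It describes no adjustment for vignette and no contrast within a case.

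**The concern.** Positive agreement is computed on three cases and negative agreement on five different ones. If the three positive cases also look riskier on their clinical features, physicians who ignored EsoGuard altogether would refer them more often. Both agreement figures could then look favourable with no influence from the test. Nothing in the documents says that the positive and negative cases are matched to each other on risk.

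The synopsis says the trial is meant to supply clinical utility evidence for reimbursement, and readers are likely to take high agreement as a sign that the result drives referral. The trial already randomizes physicians to three versions, but that randomization yields no estimate of how a positive rather than a negative result changes the decision on the same patient.

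**Working it through.** The plan gives no figure to reproduce. Section 7.2 names a minimum of 100 providers without alpha, power or effect size, and says that no data on the expected referral rate exist. All referral rates below are therefore assumptions, as is an equal split over A, B and C.

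**1. Case by result in Round 2** (99 physicians, 33 per version; cases from section 6.2)

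| Cases | Responses with negative result, per case | Responses with positive result, per case |
|---|---|---|
| 5 negative cases | 99 | 0 |
| 3 positive cases | 0 | 33 |

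Every case has an empty cell. With 100 physicians the totals are 5 × 100 = 500 negative and 1 × 100 = 100 positive responses.

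**2. Can the result effect be estimated within Round 2?** A model with one effect per case has rank 8. Adding a result term leaves the rank at 8, because the result indicator is the sum of the three positive-case indicators. Result and case are completely aliased.

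**3. What do both rounds together add?** Profile effects plus round have rank 9. Adding a positive-result term gives 10, but that term is identical to an interaction of positive-case group with round. Adding a negative-result term as well leaves 10, because it equals round minus the positive-result term. Without further assumptions, the effect of a negative result cannot be told apart from the effect of being in Round 2.

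**4. Agreement when the result has no effect.** Let *n* and *p* be the referral rates for the negative and positive cases on clinical features alone. Then:

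- positive agreement = *p*; negative agreement = 1 − *n*
- concordance = [5(1 − *n*) + *p*]/6
- PPV = *p*/(5*n* + *p*)
- NPV = 5(1 − *n*)/[5(1 − *n*) + 1 − *p*]

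| *n* / *p* (assumed) | Referral difference (*p* − *n*) | Positive / negative agreement | Concordance | PPV | NPV | Round 1 to 2 change |
|---|---|---|---|---|---|---|
| 50% / 50% | 0 points | 50% / 50% | 50% | 17% | 83% | 0 |
| 40% / 60% | 20 points | 60% / 60% | 60% | 23% | 88% | 0 |
| 40% / 70% | 30 points | 70% / 60% | 62% | 26% | 91% | 0 |
| 30% / 80% | 50 points | 80% / 70% | 72% | 35% | 95% | 0 |
| 20% / 90% | 70 points | 90% / 80% | 82% | 47% | 98% | 0 |

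The agreement statistics move with case mix alone. The last column stays at 0 because the same profiles, with the same rates, appear in Round 1.

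**5. Precision if the positive result is rotated over three common profiles.** With 100 physicians, each of profiles 1 to 3 is positive for about a third and negative for about two thirds. In total that is about 100 positive and 200 negative responses. The half-width is 1.96 × √[*p*₁(1 − *p*₁)/100 + *p*₀(1 − *p*₀)/200], where *p*₁ and *p*₀ are the referral rates with a positive and a negative result.

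- 90% vs 20%: 1.96 × √(0.0009 + 0.0008) = 1.96 × 0.0412 = 8.1 points
- 50% vs 50%: 1.96 × √(0.0025 + 0.00125) = 1.96 × 0.0612 = 12.0 points

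Both ignore clustering of responses within physician.

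**The case against.** The strongest reply is that the plan has its own control for case mix. Section 6.1 gives every Round 2 risk profile a counterpart without a result, and section 7.3 defines the primary measure as the change between rounds. A stable profile effect cancels in that change, as the last column of the table shows. This stands. A reader might infer from the fixed results that the primary comparison is itself confounded with case profile; the documents do not support that. What the change does carry is the fixed round order, the information package, the reworded case text, and any shift between rounds that differs by profile.

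A reader might also infer that the randomization misses the very factor the primary objective names. That is too strong as well. Section 7.3 measures decisions with the test against decisions without it. Positive versus negative is a different contrast, and rotating results would not randomize test against no test.

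Three further replies stand in part:

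- **Summaries only.** Section 7.3 offers the agreement figures as summaries and not as effect estimates. They are nevertheless listed under the primary objective with no caution about case mix.
- **Existing data.** The change in positive cases could be set against the change in negative cases, which removes education and repeat effects common to both. This assumes those effects are equal in the two groups of cases, and section 7.3 does not plan it.
- **Self-report.** Physicians are asked for each case whether the result influenced them. That is useful, but it is their own account and not a comparison of decisions.

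**Conclusion.** The point holds for the Round 2 positive-versus-negative contrast and for all five agreement statistics in section 7.3. There the confounding with case profile is complete, and it follows from section 6.2 without any assumption about rates. It does not extend in this form to the primary Round 1 to Round 2 change, where the remaining problems are order, education and rewording.

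The size and direction of any bias in the agreement statistics are unknown. The apparent separation with no test effect runs from 0 to 70 points over the assumed rates, and would be small if the positive and negative cases were alike in risk. The documents do not give the vignettes' risk levels. The plan should be changed: the primary measure can still be computed, but a randomized estimate is being forgone that needs no extra physicians.

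**What to change.** **Section 6.2.** Use the same six profiles in all three questionnaires and rotate the positive result over profiles 1 to 3. Version A shows profile 1 as positive, B profile 2 and C profile 3; all other results are negative. Each physician still sees one positive and five negative cases.

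**Sections 6.1 and 6.2.** Change the count of 8 cases to 6 in both, so that Round 1 still matches Round 2.

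**Section 7.3.** Add three items:

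- the randomized difference in referral (positive minus negative result) on profiles 1 to 3 within Round 2, adjusted for profile and allowing for clustering by physician;
- agreement statistics for profiles 1 to 3 reported separately, because profiles 4 to 6 remain always negative and the overall figures stay partly confounded;
- the Round 1 to Round 2 change reported separately for positive-result and negative-result cases, because negatives make up 5 of every 6 responses in the pooled change.

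The new contrast compares identical case text in the same round, after the same information package. It estimates positive versus negative result, not test versus no test. On its own it cannot say whether positive results raise referral or negative results lower it, and it does not free the round comparison from education and order.

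**Cost.** No extra participants or rounds. The vignette set shrinks from eight profiles to six in both rounds, and the three rotated profiles must be clinically plausible with either result.

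### The three Round 2 closing ratings use asymmetric end anchors, and the third asks two things at once: a minor wording fault, cheap to correct before fielding

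*Combined protocol and SAP*

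**What the plan says.** Section 6.2 (Round 2 Intervention) ends with three ratings, asked of each participant "at the end of round two (scale 1 very low to 5 high"). They are:

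1. understanding: "Rate your understanding of EsoCheck/EsoGuard and its indications";
2. own use: "How likely are you to use EsoCheck/EsoGuard for BE screening in your own practice";
3. a third item: "How likely are you to refer this technology to others or use in their practices".

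Only points 1 and 5 have labels; nothing is said about points 2 to 4. Section 6.1 (Round 1 Control) treats its two five-point knowledge items differently and labels every point: "1 = not knowledgeable at all; 2 = not very knowledgeable; 3 = somewhat knowledgeable; 4 = very knowledgeable; 5 = expert".

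For analysis, section 7.3 says: "The baseline and self-assessment questions, Round 1 Control, and Round 2 Intervention, will be reported in a table with counts and percentages". It gives no cut-off, mean, test or pooling rule for the closing items, and does not say whether categories may be combined.

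**The concern.** There are two separate faults of wording.

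First, a scale that starts at an extreme and stops short of one at the other end invites respondents who mean 'high' to choose 5, the same point that those who mean 'very high' must choose. If anchoring has any effect, the direction it suggests is upward, which favours the product.

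Second, the third item collects one number for two acts. Two physicians who both answer 4 may have answered different questions. The word 'refer' adds to the doubt, because everywhere else in the questionnaire it means sending a patient for endoscopy.

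The closing ratings are the only place where the trial asks about understanding of EsoCheck/EsoGuard or about intended uptake. The Round 1 knowledge items concern Barrett's esophagus, esophageal adenocarcinoma and screening options, and the influence question in Round 2 concerns a single referral decision. The synopsis gives reimbursement as the purpose of the utility data, and readers with that purpose are likely to look at stated likelihood of use. The ratings are also taken once only, so a bias from the anchors cannot cancel in a comparison between rounds, as a constant bias could for the risk and referral questions.

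**Working it through.** The plan states no figure on this point, so there is nothing to reproduce. The check is a reading of the text, followed by an illustration on assumed numbers.

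**Reading check**

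- *Anchors.* Section 6.2 pairs 'very low' with 'high'. The counterpart of 'very low' would be 'very high'. With points 2 to 4 unlabelled, nothing in the text separates 'high' from 'very high'. The asymmetry is therefore on the page.
- *Third item.* Item 2 already asks about the physician's own practice. If item 3 means recommending to others for use in those others' practices, the 'or' is wrong. If it means recommending or using, 'their' does not fit a respondent rating personal use, and the second half overlaps item 2. On neither reading does the printed sentence ask one clear question.
- *Item 2.* It asks a single question and can be read as it stands, apart from the shared anchors.
- *Role in the analysis.* For the primary objective, section 7.3 specifies "assessing the change in the percentage/rate of virtual patient cases who will be referred for endoscopy in the intervention round compared to the control round"; for the secondary objective it uses the shift in assessed risk between rounds. The agreement statistics and the self-reported influence proportion use the per-vignette questions. None of these draws on the closing ratings.

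**Illustration (assumed distribution, not from the documents)**

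Suppose a symmetric scale would give 10, 20, 30, 25 and 15% at points 1 to 5. Let *f* be the unknown share of respondents who move up one point because the top label is weaker.

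- Only 4 to 5 moves: share at 5 = 15 + 25*f*; share at 4 or 5 stays at 25 + 15 = 40.
- 3 to 4 also moves: share at 4 or 5 = 40 + 30*f*.

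| *f* | Share at 5 | 4 or 5, only 4→5 moves | 4 or 5, 3→4 also moves |
|---|---|---|---|
| 0 | 15% | 40% | 40% |
| 0.10 | 17.5% | 40% | 43% |
| 0.25 | 21.25% | 40% | 47.5% |
| 0.50 | 27.5% | 40% | 55% |

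The extreme case, *f* = 1, would put 15 + 25 = 40% at point 5.

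For scale, the 95% half-width with the protocol's minimum of 100 participants is 1.96 × √(0.40 × 0.60 / 100) = 0.096, or 9.6 points, for a share of 40%. For a share of 15% it is 1.96 × √(0.15 × 0.85 / 100) = 0.070, or 7.0 points. A shift at *f* = 0.10 (2.5 points at category 5) would be lost in sampling error; one at *f* = 0.50 (12.5 points) would not. The documents give no means of choosing between them.

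No similar calculation is possible for item 3, because the split between its two meanings is not observed.

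**The case against.** The other side has several good points.

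- *The scale text may be shorthand.* It is one parenthesis covering three items, and the fielded online questionnaire is not in the documents. 'High' may be a slip for 'very high', and 'or use' a slip for 'for use'. This stands as a caution: the point concerns the protocol as written, and if the live form already differs, only the protocol needs correcting.
- *Respondents may treat 5 simply as the maximum.* This also stands, and it is why a nil effect cannot be excluded. A reader might infer that the uptake ratings will be inflated. The documents do not support that; upward drift is possible, but is neither shown nor sized.
- *The items are ancillary.* This stands. A reader might infer that a planned adoption endpoint is compromised. Section 7.3 names no such endpoint or table and no threshold for counting a rating as favourable. It plans a descriptive tabulation of all baseline and self-assessment questions. If every category is shown, readers can see the whole distribution.
- *Intended adoption is asked cleanly in item 2.* This stands, so any claim that the uptake ratings as a group cannot be interpreted goes too far. The ambiguity is confined to item 3.
- *A neutral midpoint is a matter of taste.* This stands. Ratings of understanding or likelihood can run from less to more without a neutral point, so labelling all five points is optional.

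What remains is that the printed anchors do not match, the printed third item asks two things, and no other section repairs either.

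**Conclusion.** The point holds as a minor one and is best classed as a cheap improvement. The closing ratings may be shifted upward by an amount that the documents do not determine. In the illustration the top category runs from 15% (no effect) to 27.5% (half of the 4s move), and all of that rests on an assumed distribution and an unknown *f*. The third item's rating cannot be attributed to recommending or to using. The primary and secondary results are not affected. The conclusion assumes that the questionnaire is fielded with the wording printed in section 6.2.

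**What to change.** Before the Round 2 questionnaire is sent:

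1. Make the end anchors symmetric: 1 = very low, 5 = very high. Labels for points 2 to 4, as in the Round 1 knowledge items, are optional.
2. Replace the third item by one question, for example: *How likely are you to recommend EsoCheck/EsoGuard to colleagues for use in their practices?* Own use stays with item 2.
3. State in section 7.3 that all five categories of each closing item will be reported, without collapsing.

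The cost is a small wording change to the questionnaire and one sentence in the analysis section. Sample size, randomization, vignettes and the analysis of both objectives stay as they are. If the items have already been fielded as printed, print the exact wording and anchors beside the results, and do not present item 3 as a measure of either act alone.
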